6.2.6 Exposure to Study Drug

Duration of exposure to study drug will be calculated as follows:

- Date of last dose (or the date of completion/termination if not present) minus the date of first dose + 1.

The exposure calculation will not take into account breaks in therapy.

	Confidentiality Statement	
This document	may not be duplicated, copied, altered or removed from company	

Controlled Quality Management Document

Sponsor:

Pliant Therapeutics Inc.

Protocol Number:

PLN-74809-PSC-203

STATISTICAL ANALYSIS PLAN**6.2.7 Study Drug Compliance**

Study drug compliance will be calculated by comparing the amount of drug dispensed and drug returned for each participant as follows:

- Number [REDACTED] taken = Total dispensed – Total returned (if the number returned is missing, a value of 0 will be used).
- Expected number [REDACTED] = Number of days on study (calculated as per Section 6.2.6 for duration of exposure) × Number [REDACTED] for the relevant study part and dose group (per the table below).

Compliance (%) = (Number [REDACTED] taken / Expected number [REDACTED]) *100

[figure not shown]

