- If the stop date occurs on or after the start of study drug or the event / concomitant medication is ongoing, and the year is the same as the year of first dosing the start date will be imputed as the date of the first dose of study drug whichever is latest. If the year is different from the year of first dosing “01-Jan” will be used.
- If the stop date occurs before the start of study drug, the start date of the event / concomitant medication will be imputed as the “01-Jan” of the same year.

Partial start date (month and year present, but day missing)

- If the stop date occurs on or after the start of study drug or the event / concomitant medication is ongoing, the start date will be imputed as the first day of the same month and year unless this partial start date is in same month as the first dose of study drug in which case the date of first dose of study drug will be used.
- If the stop date occurs before the start of study drug, the start date will be imputed as the first day of the month and year of the partial stop date.

If the start time is missing it will be imputed only in the case where the start date of the concomitant medication / event corresponds to the date of the first dose of study drug. The time will be imputed as the same time as the first dose of study drug. In all other cases the time will not be imputed.

Missing Date of Last Dose

If date of last dose is not present, the date of completion/termination will be imputed as the date of last dose for calculation of study drug exposure.

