6.9 Participant Disposition

The overall total of participants in the screened population will be summarized. The number of participants randomized will be summarized by treatment group and overall.

Participant disposition will be summarized by treatment group and overall for the safety population, as follows:

- The number of participants in each analysis population (Safety, PK, and PD).
- The number of participants who complete the study drug.
- The number of participants who discontinue the study drug and the reason for discontinuation of study drug.
- The number of participants who complete the study.
- The number of participants who withdraw from the study and the reason for withdrawal.

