6.16 Study Drug Compliance

Compliance (%) will be calculated for each participant and summarized by treatment group and overall. All compliance and study drug accountability data will be listed.

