6.20 Adverse Events

AE analyses will be presented by the actual treatment received for the Safety Population.

[REDACTED]

AEs will be collected from the time of informed consent through completion of the participant's last study visit.

A treatment-emergent adverse event (TEAE) is defined as:

- Any AE that has an onset on or after the first dose of study drug through completion of the last study visit.
- Any pre-existing AE that has worsened in severity on or after the first dose of study drug through completion of the last study visit.

AEs occurring prior to first dose of study drug are considered non-treatment emergent and will be listed only.

The Investigator will determine the relationship of the AE to treatment (related, not related). If an AE has missing relationship it is assumed to be related to the study drug for analysis purposes.

Severity of the AE will be graded using the Common Terminology Criteria for Adverse Events (CTCAE) grading system (Version 5.0): Grade 1 (mild), Grade 2 (moderate), Grade 3 (severe), Grade 4 (life-threatening), Grade 5 (fatal). Grade 3 (severe) will be assumed for an AE with missing grade.

An overall summary of AEs (number of participants with an event) will be presented by treatment group and overall, for the following:

- TEAE

[REDACTED]

[REDACTED]

Controlled Quality Management Document

Sponsor: Pliant Therapeutics Inc.

Protocol Number: PLN-74809-PSC-203

STATISTICAL ANALYSIS PLAN

Confidentiality Statement

This document [REDACTED] may not be duplicated, copied, altered or removed from company
without prior approval [REDACTED].

Controlled Quality Management Document

Sponsor:

Pliant Therapeutics Inc.

Protocol Number:

PLN-74809-PSC-203

STATISTICAL ANALYSIS PLAN

- TEAE related to study drug
- TEAE Related to a Study Procedure
- Serious TEAE
- Serious TEAE Related to Study Drug
- TEAE of CTCAE Grade 3 or Higher
- TEAE of CTCAE Grade 3 or Higher Related to Study Drug
- TEAE Leading to Interruption of Study Drug
- TEAE Leading to Withdrawal of Study Drug
- TEAE Leading to Early Termination from Study
- TEAE Leading to Death

Summaries of TEAEs (number of participants with an event) will be presented by system organ class and preferred term by treatment group for the following:

- TEAE
- TEAE Related to Study Drug
- Serious TEAE
- Serious TEAE Related to Study Drug
- TEAE Related to a Study Procedure
- TEAE of CTCAE Grade 3 or Higher
- TEAE of CTCAE Grade 3 or Higher Related to Study Drug

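### SAP Section 6.2.7 scores a missing return count as all dispensed drug taken, so with the denominator fixed the compliance error is zero or upward, never downward (minor)

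*SAP*

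**What the plan says.** SAP Section 6.2.7 defines the number taken as total dispensed minus total returned, with the instruction "if the number returned is missing, a value of 0 will be used". Compliance is that number as a percentage of the expected number, which is a count of days times the daily number for the study part and dose group. The count of days is given as "Number of days on study (calculated as per Section 6.2.6 for duration of exposure".

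Section 6.2.6 runs exposure from first to last dose, both days included, and states: "The exposure calculation will not take into account breaks in therapy". Breaks are foreseen, because the overall adverse event summary in Section 6.20 has a line for "TEAE Leading to Interruption of Study Drug".

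Where the last-dose date is absent, Section 6.2.5 says that "the date of completion/termination will be imputed as the date of last dose for calculation of study drug exposure". It does not say completion of what. Section 6.9 reports two separate items, "The number of participants who complete the study drug" and "The number of participants who complete the study".

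Section 6.16 summarises compliance by treatment group and overall, and adds: "All compliance and study drug accountability data will be listed".

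**The concern.** A missing return count is an unknown. The rule turns it into a known zero and so gives the participant the highest intake that the dispensing record allows. The error has only one possible direction.

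Two consequences follow from the SAP's own definitions:

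- Break days are not removed from the expected number, so the score of an interrupted participant depends on whether the leftover drug was counted. Equal intake can give different compliance.
- A participant who stops early with a known last-dose date has a short denominator. If the leftover supply was not counted, the numerator is too large for it and the score passes 100%.

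At stake is the reliability of the compliance summary, which a reader uses to judge whether the dose groups took the drug as planned. A value above 100% draws attention to itself. A false 100% looks like perfect adherence, and the SAP text asks for no count of participants scored this way.

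**Working it through.** **Inputs.** From SAP Section 1: screening up to 42 days; treatment of 12 weeks (84 days) in Parts 1 and 2, and 24 to 48 weeks (168 to 336 days) in Part 3; 28 days of follow-up. From Section 5: 21 participants per dose group and 7 on placebo alongside each, so 4 × 7 = 28 in pooled placebo and 4 × 21 = 84 on active drug. The daily number cancels in the ratio, so everything is in days' supply. The supply interval, any overage and the frequency of missing counts are not shown; values for these are assumptions.

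**The plan's own figure.** 42 + 84 + 28 = 154 days, as Section 1 states for Parts 1 and 2. Likewise 42 + 168 + 28 = 238 and 42 + 336 + 28 = 406 for Part 3.

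**Direction of the error.** Let D be dispensed, R the unused amount and E the expected number. True compliance is 100 × (D − R)/E. With R missing, the SAP gives 100 × D/E. The error is 100 × R/E, which cannot be negative.

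**Size, 84-day completer, D = E = 84, u days' supply unused and uncounted.** True compliance is (84 − u)/84, the SAP score is 100%, and the shift of a group mean is the gap divided by n.

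| u | True | Gap (points) | n = 21 | n = 28 | n = 84 |
|---|---|---|---|---|---|
| 7 | 91.7% | 8.3 | 0.40 | 0.30 | 0.10 |
| 14 | 83.3% | 16.7 | 0.79 | 0.60 | 0.20 |
| 42 | 50.0% | 50.0 | 2.38 | 1.79 | 0.60 |

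The last row is an upper case: half taken throughout and every count missing. Over 168 days the gaps for 7 and 14 days halve to 4.2 and 8.3 points, or 0.20 and 0.40 on a mean of 21.

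**Same break, different score.** With a 14-day break in 84 days, a counted return gives 70/84 = 83.3%. No count gives 84/84 = 100%.

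**Early stop.** With last dose on day d and u days' supply left uncounted, the score is (d + u)/d. For assumed d = 42: 49/42 = 117% with u = 7, and 56/42 = 133% with u = 14.

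**Overage.** If 10% or 20% more than E is dispensed, a missing count gives 110% or 120% whatever was taken. At true 80% the error is then 30 or 40 points, against 20 without overage.

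**The last-dose date.** If the substitute is the end of drug, a completer's exposure is unaffected. If it is the end of study, 28 off-drug days are added, and full compliance reads 84/112 = 75.0%, 168/196 = 85.7% or 336/364 = 92.3%.

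**The case against.** The rule is explicit, reproducible and the same in every arm, and treating unreturned drug as taken is a recognisable accountability convention. The SAP lists all accountability data, so missing counts can be found, and the table shells, which might contain a tally, are not at hand. The false 100% needs dispensed to equal treatment days; with overage the score exceeds 100% and the maximum in the Section 6.8.3 summary could reveal it. Finally, dropping participants without counts can also leave the mean too high. All of this stands, and it is why the point is minor.

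It does not rescue the rule as the only summary. Let a fraction p lack counts, with true mean t, while the counted mean is c and the imputed score is s. Leaving them out gives an error of p(c − t); scoring them gives p(s − t). If c is at most 100%, dispensing at least meets the expected number (so s is at least 100%) and non-returners are no more adherent than returners (t at most c), then leaving them out is never further from the truth. If non-returners are the more adherent, the order can reverse, which is a reason to show both.

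A reader might infer more than the text supports:

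- **That reported compliance is always too high.** The sign holds only with the denominator fixed. If the last-dose date is also missing and is filled with the end of study, an 84-day completer (D = 84) scores 75% whatever was taken: 25 points too low at true 100%, 25 too high at true 50%.
- **That the date rule is itself an error.** The cues conflict. Section 6.2.5 speaks of drug exposure, while Section 6.2.7 speaks of days on study and Section 6.20 ties early termination to the study. Under the end-of-drug reading a completer's error is zero.
- **That endpoints or populations are affected.** No visible text makes compliance an endpoint or a criterion for an analysis population.

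**Conclusion.** The point holds as a minor one. Section 6.2.7 assigns the maximum possible intake where intake is unknown, so its error, for a given denominator, is zero or upward. Equal intake can score 83.3% or 100% depending only on whether leftovers were counted, and an early stopper can exceed 100%.

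Only the descriptive compliance summary is touched, and only through participants without a return count. The figure of 0.4 to 0.8 points on a mean of 21 is per affected participant. It assumes 7 or 14 uncounted days over 84 days and dispensing equal to treatment days. The total effect cannot be given, because the number of missing counts is unknown. The unnamed completion date is a wording gap, not a demonstrated error.

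**What to change.** 1. In Section 6.2.7, for the main summary, treat compliance as missing when the return count is missing.
2. Report the number of such participants per treatment group.
3. Show the summary under the present missing = 0 rule alongside, flagged as a sensitivity summary.
4. As a clarification only, state in Sections 6.2.5 and 6.2.6 whether the substitute date is the end of study drug or the end of study, since the second adds the 28 off-drug days to a completer's exposure and compliance denominator.

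The cost is SAP wording and minor programming on totals already used. The drawback is that some participants, including those lacking only one of several counts, have no value in the main summary. The remaining mean may also still be too high if non-returners are less adherent. The count and the sensitivity summary let the reader judge that.

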**6.2.8 Inexact Values**

In the case where a variable is recorded as “> x”, “≥ x”, “< x” or “≤ x”, a value of x will be taken for analysis purposes. All data will be presented as is for listing purposes.

6.2.9 Imperial to Metric Unit Conversion

Temperature collected in degrees Fahrenheit (°F) will be converted degrees Celsius (°C) using the following conversion calculations:

- $x ({}^{\circ}C) = [x ({}^{\circ}F) - 32] / 1.8$

6.3 Partial Mayo Score for Inflammatory Bowel Disease (IBD)

The partial Mayo score, range 0-9, with higher scores implying more severe disease will be derived as follows:

Partial Mayo Score = Stool frequency score (0-3) + Rectal bleeding score (0-3) + Physicians' global assessment (0-3).

Confidentiality Statement

This document [REDACTED] may not be duplicated, copied, altered or removed from company [REDACTED].

Controlled Quality Management Document

Sponsor: Pliant Therapeutics Inc.

Protocol Number: PLN-74809-PSC-203

STATISTICAL ANALYSIS PLAN

[REDACTED]

[REDACTED]

[REDACTED]

||
[REDACTED]
[REDACTED]
[REDACTED]
[REDACTED]

[REDACTED]

[REDACTED]

[REDACTED]

[REDACTED]

[REDACTED]

[REDACTED]
[REDACTED]

[REDACTED]
[REDACTED]

[REDACTED]

[REDACTED]

[REDACTED]

[figure not shown]
[REDACTED]

[REDACTED]);

Confidentiality Statement

This document [REDACTED] may not be duplicated, copied, altered or removed from company [REDACTED]
without prior approval [REDACTED]

		Controlled Quality Management Document	
		Sponsor:	Pitant Therapeutics Inc.
		Protocol Number:	PLN-74809-PSC-203
STATISTICAL ANALYSIS PLAN			

6.6 Early Termination Assessments

Unscheduled early termination assessments will not be summarized unless the early termination visit falls on a scheduled visit.

6.7 Unscheduled Visits

Only scheduled post baseline values will be tabulated. Post baseline repeat / unscheduled assessments will not be summarized but will be listed in the relevant appendices to the CSR.

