6.2.2 Body Mass Index

Body mass index (BMI) will be calculated as follows:

$$\text{BMI (kg/m}^2\text{)} = \text{Weight at Screening (kg)} / [\text{Height at Screening (m)}^2]$$

	Confidentiality Statement	
This document		may not be duplicated, copied, altered or removed from company

Controlled Quality Management Document

Sponsor: Pliant Therapeutics Inc.

Protocol Number: PLN-74809-PSC-203

STATISTICAL ANALYSIS PLAN**6.2.3 Baseline and Change from Baseline**

Baseline is defined as the last non-missing value before the participant receives the first dose of study drug. Change from baseline is defined as the difference between baseline and any post-baseline records.

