6.18 Pharmacodynamic Analyses

Biomarker analyses will be presented by treatment group for the PD Analysis Population per Table 1.

Table 1. PSC Biomarkers

Biomarker	Timepoints (Parts 1 and 2)	Timepoints (Part 3)
PRO-C3 [REDACTED]	Baseline, Weeks 2, 4, 8, 12 and Week 16 (off-treatment)	Baseline, Weeks 2, 4, 8, 12, 24, EOT (variable weeks) and EOS (variable weeks)
ELF [REDACTED]	Baseline, Weeks 4 and 12	Baseline, Weeks 4, 12 and 24
[REDACTED]	[REDACTED]	[REDACTED]
[REDACTED]	[REDACTED]	[REDACTED]
[REDACTED]	[REDACTED]	[REDACTED]
ALP, [REDACTED]	Baseline, Weeks 2, 4, 8, 12 and Week 16 (off-treatment)	Baseline, Weeks 2, 4, 8, 12, 18, 24, 32, 40, 48 and 52 (off treatment)

Biomarker results obtained from plasma, or serum samples will be summarized using descriptive statistics by treatment group and visit for each parameter. Actual biomarker concentration at each visit, the absolute change from baseline and relative change (percentage change) from baseline will be presented. [REDACTED]

[REDACTED]

Confidentiality Statement

This document [REDACTED] may not be duplicated, copied, altered or removed from company [REDACTED] without prior approval [REDACTED]

Controlled Quality Management Document

Sponsor:

Pliant Therapeutics Inc.

Protocol Number:

PLN-74809-PSC-203

STATISTICAL ANALYSIS PLAN

If provided, the result adjusted for dilution factor will be used in summaries and listings. Any samples hemolyzed, received ambient, or with a note indicating improper storage will be excluded from summaries and listed only. If a sample has been excluded, then the change from baseline for that sample will also not be calculated.

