6.18.1 Biomarkers with One Post Baseline Assessment

The following endpoints include only one post baseline assessment for Parts 1, 2 and 3 Week 12 interim analysis:

Endpoints measured at baseline and only one post baseline visit will be analyzed by the analysis of covariance (ANCOVA).

The LS means, corresponding SEs, and 95% CI for each treatment group will be obtained from the model. An estimate for the LS mean difference (PLN-74809 vs. placebo), corresponding SE, 95% CI, and p-value for each dose group will also be presented. Each individual active group will be compared to pooled placebo (Parts 1, 2 and 3).

Actual biomarker concentrations will be presented as a box plot by treatment group for each parameter. In addition, line plots using the LS estimated values and corresponding SE will also be presented.

Confidentiality Statement

This document [REDACTED]
without prior approval

[REDACTED] may not be duplicated, copied, altered or removed from company [REDACTED]

Controlled Quality Management Document

Sponsor:

Pliant Therapeutics Inc.

Protocol Number:

PLN-74809-PSC-203

STATISTICAL ANALYSIS PLAN**6.18.2 Biomarkers with 2 or more Post Baseline Assessments**

The following endpoints include at least two post baseline assessments:

- Liver function parameters: ALP
- Liver fibrosis parameters: PRO

Endpoints measured at baseline and at least two post baseline visits will be analyzed using a mixed-effect model repeated measures (MMRM)

The LS means, corresponding SEs, and 95% CI for each treatment group at each visit will be obtained from the model. An estimate for the LS mean difference (PLN-74809 vs. placebo), corresponding SE, 95% CI, and p-value for each dose group at each visit will also be presented. Each individual active group will be compared to pooled placebo (Parts 1, 2 and 3).

Confidentiality Statement

This document [REDACTED] may not be duplicated, copied, altered or removed from company [REDACTED] without prior approval [REDACTED]

		Controlled Quality Management Document	
		Sponsor:	Pitant Therapeutics Inc.
		Protocol Number:	PLN-74809-PSC-203
STATISTICAL ANALYSIS PLAN			

[REDACTED]

[REDACTED]

[REDACTED]

[REDACTED]

For biomarkers with at least 2 postbaseline scheduled assessments, LS Mean change from baseline will be presented as a line plot showing baseline (0) and the LS mean (\pm SE) concentration at each post-dose visit by treatment group for each parameter.

[REDACTED]

[REDACTED]

[REDACTED]

[REDACTED]

[REDACTED]

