- TEAE Leading to Withdrawal of Study Drug
- TEAE by SOC, PT and Maximum Grade (incidence only)
- [REDACTED]

The following listings of TEAEs will be presented in Section 14.3.2 of the CSR.

- TEAE Leading to Withdrawal of Study Drug
- TEAE Leading to Early Termination from Study
- TEAE Leading to Death
- Serious TEAE

System organ class will be presented in descending order of frequency in the pooled PLN-74809 group and then alphabetically. Preferred terms will be displayed in descending order of frequency in the pooled PLN-74809 group and then alphabetically.

Confidentiality StatementThis document [REDACTED]
without prior approval [REDACTED]

may not be duplicated, copied, altered or removed from company [REDACTED]

Controlled Quality Management Document

Sponsor:

[figure not shown]
Pliant Therapeutics Inc.

Protocol Number:

PLN-74809-PSC-203

STATISTICAL ANALYSIS PLAN

For summary by severity, participants reporting more than one AE per system organ class and preferred term will only be counted once for the most severe event.

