6.20.2 Laboratory Data

Descriptive statistics of the observed values and change from baseline will be presented by treatment group and visit for each continuous hematology, serum chemistry, coagulation, and urinalysis parameter. Shift tables for the change from baseline in categorical parameters will be presented in the natural order of the outcome where possible.

Summaries and listings will be presented using the Système International (SI) unit for each parameter as received from the analytical laboratory.

Each measurement (for continuous data where provided) will be classified as below, within, or above normal range based on ranges supplied by the laboratory used. Shift tables in relation to the normal range from baseline to each follow-up visit will be presented.

Clinical laboratory test parameters outside the reference ranges will be flagged. The incidence of treatment-emergent laboratory abnormalities (on or after first dose of study) will be summarized by severity and treatment group.

All individual laboratory data (including pregnancy testing data) will be listed.

Confidentiality StatementThis document [REDACTED]
without prior approval [REDACTED]

[REDACTED] may not be duplicated, copied, altered or removed from company [REDACTED]

Controlled Quality Management Document		
	Sponsor:	Pliant Therapeutics Inc.
	Protocol Number:	PLN-74809-PSC-203

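### As worded, the SAP keeps off-schedule worst values out of the laboratory abnormality incidence table and defines treatment-emergent for that table by timing alone

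*SAP*

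**What the plan says.** Section 6.7 sets a general rule: "Only scheduled post baseline values will be tabulated". Repeat and unscheduled post-baseline results go to listings only. Section 6.6 adds: "Unscheduled early termination assessments will not be summarized unless the early termination visit falls on a scheduled visit". Neither section makes an exception for safety data.

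Section 6.20.2 plans descriptive statistics and shift tables by visit. It also plans a display with no visit dimension: "The incidence of treatment-emergent laboratory abnormalities (on or after first dose of study) will be summarized by severity and treatment group". It does not say that this table departs from Sections 6.6 and 6.7.

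Two other definitions matter. Section 6.2.3 states: "Baseline is defined as the last non-missing value before the participant receives the first dose of study drug". That is not restricted to scheduled draws. For adverse events, the second part of the definition in Section 6.20 is: "Any pre-existing AE that has worsened in severity on or after the first dose of study drug through completion of the last study visit". Section 6.20.2 has no matching requirement for laboratory values.

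**The concern.** There are two separate problems. Sections 6.6 and 6.7 decide which values can enter the incidence table. Section 6.20.2 decides which of those count.

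**Entry.** A scheduled-only rule suits a by-visit summary, where an extra draw has no column to go in. That reason does not apply to a participant-level count of abnormalities. Off-schedule draws are often taken because a result needs checking or a participant is leaving, so they are a likely place to find a worst value. The rule is also one-sided: a repeat before dosing can set baseline, but a repeat after dosing cannot register an abnormality.

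**Counting.** Read literally, an abnormality already present before dosing, and no worse since, counts as treatment-emergent. The trial enrols people with PSC and suspected liver fibrosis (Section 1), so abnormal liver tests at baseline are plausible, although the SAP gives no rate.

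In the readable text, this table is where laboratory severity rates are set side by side by arm. Section 7 has both interim analyses cover all planned final analyses, so the same rule applies there.

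**Working it through.** The concern rests on wording, and the SAP states no figure for it to reproduce. The arithmetic only shows scale.

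**1. Group sizes (Section 5).** 21 active and 7 placebo per dose, four doses: 4 × (21 + 7) = 112, matching the stated total. Final pooled placebo is 4 × 7 = 28, and all active participants number 4 × 21 = 84. At the Parts 1 and 2 interim, pooled placebo is 3 × 7 = 21.

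**2. Effect of participants whose worst value is only off schedule.**

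| Group | Calculation | Change in rate |
|---|---|---|
| One dose group, one participant | 1/21 | 4.8 points |
| One dose group, two participants | 2/21 | 9.5 points |
| Pooled placebo, final, one participant | 1/28 | 3.6 points |
| Pooled placebo, Parts 1 and 2 interim, one participant | 1/21 | 4.8 points |
| All active, one participant | 1/84 | 1.2 points |

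**3. Spacing of scheduled draws (ALP, Table 1 in Section 6.18).** In Part 3, draws at weeks 0, 2, 4, 8, 12, 18, 24, 32, 40 and 48 are 2, 2, 4, 4, 6, 6, 8, 8 and 8 weeks apart. In Parts 1 and 2, weeks 0, 2, 4, 8, 12 and 16 give gaps of 2, 2, 4, 4 and 4. An off-schedule draw can therefore be the only ALP value in a span of up to 8 weeks late in Part 3, and up to 4 weeks elsewhere.

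**4. Illustration of the entry rule, assumed rates.** Let p be the true incidence of a given abnormality and s the share of cases seen only off schedule. The tabulated incidence is p(1 − s), and the chance that a group of 21 shows at least one case is 1 − [1 − p(1 − s)]^21.

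| p | All values | s = 10% | s = 25% | s = 50% |
|---|---|---|---|---|
| 5% | 0.659 | 0.620 | 0.552 | 0.412 |
| 10% | 0.891 | 0.862 | 0.805 | 0.659 |

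The SAP gives neither p nor s.

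**5. Illustration of the timing-only wording, assumed rates.** Let b be the share abnormal at baseline who stay so, and q the rate of new abnormality among the rest. Literal counting gives b + (1 − b)q. Take b = 50%, with q = 5% on placebo and 20% on active:

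- Literal wording: 0.50 + 0.50 × 0.05 = 52.5% against 0.50 + 0.50 × 0.20 = 60.0%.
- New abnormalities only, same denominator: 0.50 × 0.05 = 2.5% against 0.50 × 0.20 = 10.0%.

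The difference is 7.5 points either way, but the ratio falls from 4 to 1.14 and the background is much noisier. At b = 30% the literal wording shows 33.5% against 44.0%, and at b = 70% it shows 71.5% against 76.0%. None of these rates comes from the SAP.

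**The case against.** The strongest reply is that Section 6.7 is a convention for by-visit tables, and that the parenthesis in Section 6.20.2 is this table's own inclusion rule, admitting any value after first dose. The parenthesis does set a time window. It says nothing about type of visit, however, and does not override an unqualified statement that such values are not summarized. At best, two programmers could build different tables.

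On the second problem, it can be said that treatment-emergent already implies emergence and that the parenthesis gives only the window. That may be the intent. The SAP spells out worsening for adverse events but not for laboratory values.

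Several limiting points stand:

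- Redacted or missing sections, the table list or the shells may contain an exception or another display.
- A confirmatory repeat adds nothing unless it is worse than the scheduled value.
- The 8-week gaps are known only for ALP, occur only after Week 24 and do not reach every Part 3 participant. They do not bear on the interim analyses: to Week 12, ALP gaps are at most 4 weeks.
- The rule is the same in every arm, so no bias in a particular direction is shown.
- The primary endpoint is untouched, and DSMB reporting has its own charter (Section 8).

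Mitigation is real but partial. Higher severities at scheduled visits still appear in their own rows. Section 6.18.2 gives ALP "An estimate for the LS mean difference (PLN-74809 vs. placebo), corresponding SE, 95% CI, and p-value for each dose group at each visit", but these are means at scheduled visits. Shift tables work by visit and by normal range, not by severity. TEAE tables by maximum grade catch a laboratory value only if it is reported as an adverse event. Listings hold every value but give no rates by arm.

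**Conclusion.** The concern holds on the readable text. Followed literally, the plan can understate worst laboratory severity on a secondary safety endpoint, in a trial whose primary objective is safety and tolerability. It also leaves treatment-emergent with a looser meaning for laboratory values than for adverse events.

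The scale per participant is firm given the planned group sizes: 4.8 points in a dose group and 3.6 in the final pooled placebo. How many participants would be affected, and how far the timing-only wording would blur comparisons between arms, cannot be derived from the SAP. The conclusion assumes that no unreadable part of the document makes an exception. The change should be made, with medium confidence that the text as it stands would be applied literally.

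**What to change.** - In Sections 6.6 and 6.7, limit the scheduled-only rule to by-visit descriptive summaries.
- In Section 6.20.2, base the incidence table on each participant's worst value after first dose, drawn from scheduled, unscheduled, repeat and early-termination samples.
- In the same section, define a treatment-emergent laboratory abnormality as one that is new or worse in severity than at baseline. State where the window ends, and name the laboratory severity scale unless redacted text already does: the readable text gives CTCAE for adverse events only.

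If the Parts 1 and 2 interim data have already been unblinded, Section 6 routes the change to a SAP addendum.

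The cost is a few words and minor programming, since the values are already collected and listed. Worst-severity rates may look slightly less favourable, and participants with more draws have more chances to register an abnormal value. The by-visit tables stay on scheduled values.
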